**PET/CT Quantitative Assessment of Myocardial Blood Flow Changes in
Oncologic Patients Receiving Checkpoint Inhibitor Therapy**

NCT#: NCT04538950

Protocol Version: 4.0

Date:10 November 2021

PET/CT Quantitative Assessment of Myocardial Blood Flow Changes in Oncologic Patients Receiving Checkpoint Inhibitor Therapy

Abstract (150 words or less with hypothesis)

Immune checkpoint inhibitors (ICI) are novel chemotherapeutic agents which disinhibit T-cell activity, thereby enhancing autoimmune response¹ and ushering in a new era of treatment for patients with both solid and hematologic malignancies.² Unfortunately, resultant side effects of ICI use, termed immune-related adverse events (IRAE), are difficult to both diagnose and treat resulting in high fatality rates.³ The ability to accurately detect subclinical decline in myocardial performance and the resultant initiation of targeted therapy has markedly improved the outcomes of patients prescribed the more traditional cardiotoxic chemotherapeutic agents such as anthracyclines.⁴ Consequently, means by which to detect subclinical myocardial injury is garnering increasing interest and now includes the assessment of endothelial function.⁵⁻⁷ Quantitative positron emission tomography computed tomography (PET-CT) is a highly accurate, reproducible and repeatable technique by which to assess myocardial blood flow (MBF) and endothelial function.^{8,9} For instance, recent studies have demonstrated a decrease in myocardial flow reserve (MFR) in patients receiving doxorubicin.⁷ We hypothesize that PET/CT MFR will decrease in some patients receiving ICI thereby representing early, subclinical myocardial injury and potentially serving as an early indicator of patients who might be predisposed to IRAEs.

Principal Investigator: [name] MD

Co-investigators: [name] MD, [name] MD, [name] MD, [name] [name], and [name] MD
IRB # 19-009189

A. Rationale: Brief paragraph establishing rationale

Established chemotherapeutic agents such as anthracyclines, trastuzumab and bevacizumab have proven cardiotoxic effects.¹⁰ Historically, some of these sequelae have been severe enough to render a patient's prognosis poorer than that of a patient with ischemic heart failure.¹¹ Consequently monitoring protocols designed to detect decline in cardiovascular function were initiated in the 1970s and have continued to evolve to include multigated acquisition scan (MUGA), strain echocardiography and high sensitivity troponin.^{12, 13} Early detection of chemotherapeutic cardiotoxicity paired with institution of therapy has markedly improved the prognosis of oncologic patients.^{4, 14}

Immune checkpoint inhibitors (ICI) disinhibit T-cell activity thereby allowing for a heightened antitumor immunologic response.^{1, 15} Resultant outcomes for patients with both solid and hematologic malignancies have been promising.^{2, 16, 17} However, immune-related adverse events (IRAE) have been reported secondary to administration of these agents including myocarditis (odds ratio of 11.21), cardiomyopathy and conduction abnormalities.^{18, 19} Furthermore, a fatality rate as high as 39 percent has been reported for patients who develop IRAE myocarditis.³ Approximately 75 percent of patients who develop myocarditis have normal myocardial function prior to therapy and no known preexisting cardiovascular conditions.³ When myocarditis does occur as an IRAE it typically does so in the first month.³ Unfortunately IRAEs have thus far been difficult to diagnose and to treat with leaders in the field calling for "development of guidelines for early diagnosis."³

Endothelial dysfunction has been demonstrated with the use of other multiple chemotherapeutic agents^{3, 5, 20} and is likely due either to endothelial cell death or reduced nitric oxide availability. Quantitative positron emission tomography computed tomography (PET-CT) is an emerging modality which provides a highly accurate, reproducible, repeatable, noninvasive means by which to assess total myocardial blood flow, specifically myocardial flow reserve (MFR,) including assessment of the endothelium.^{8, 9} Recently, PET-CT MFR was utilized to demonstrate a decrease in MFR in some patients after exposure to doxorubicin but not others thereby labeling them as more likely to develop cardiotoxicity.³ The current proposal seeks to utilize PET-CT MFR to assess dynamic changes in MFR that occur pre and post

initiation of ICI and thereby potentially identify early cardiotoxicity in patients who might be more prone to more devastating IRAEs such as myocarditis.

There is also considerable interest in identifying unique immune cell phenotypes in the peripheral blood that can predict which patients are most at risk for developing checkpoint inhibitor-mediated IRAEs.²¹ In the long-term, this would serve as a less invasive means of monitoring patients both before and during treatment. Thus, this proposal will also collect and analyze peripheral blood from the patients who undergo PET-CT MFR to determine if a particular T cell phenotype prior to therapy may correlate with imaging changes and cardiotoxicity of ICI.

B. Hypothesis:

PET-CT MFR will identify a certain proportion of oncologic patients being prescribed ICIs who develop microvascular damage/endothelial dysfunction. This initial study could serve as the foundation for larger evaluations of this population in determining whether or not routine surveillance can identify patients early who are at higher risk of IRAE and potentially improve outcomes.

C. Aims:

The aims of the current study are two-fold. First is to determine if ICI administration causes microvascular damage/endothelial dysfunction. If so, the second aim is to serve as a pilot study for larger trials to determine the prevalence of ICI-induced microvascular damage/endothelial dysfunction and specifically if it identifies patients who are at increased risk of IRAEs.

D. Innovation:

What is known:

- 1) Traditional chemotherapeutic agents can cause microvascular damage/endothelial dysfunction^{3, 5, 20}
- 2) Early detection of chemotherapeutic toxicity can improve outcomes⁴
- 3) PET-CT MFR can be used to detect chemotherapeutic reduction in MFR in patients receiving traditional agents such as doxorubicin³
- 4) ICI induced IRAE can cause significant morbidity and mortality

- 5) Increased lymphocyte counts and clonal expansion of CD8⁺ T cells in the peripheral blood can precede development of ICI-induced IRAE. ^{22,23}

What remains to be discovered:

- 1) Do ICIs cause microvascular disease/endothelial dysfunction?
- 2) If ICIs do cause microvascular disease/endothelial dysfunction how common is this occurrence and what is its bearing on patient prognosis?
- 3) Is there any correlation between T cell phenotypes in the peripheral blood and microvascular disease/endothelial dysfunction that occurs on ICI therapy?

E. Significance: How will this change our practice, increase our national standing, attract patients or advance our knowledge about CV disease. What is Mayo unique? (numbered list).

- 1) Cardio-oncology is a rapidly expanding field and Mayo Clinic has several clinicians at the forefront¹⁰
- 2) Oncologic patients are attracted to Mayo Clinic already for our expertise and this will further enhance the practice
- 3) Mayo Clinic is a leading center for cardiac PET and specifically PET-CT MFR⁶

E. Brief Synopsis of Methods: Very brief summary – numbered list acceptable – of what will actually be done.

- 1) Collaboration between Cardiology, Oncology and Cardiac PET to recruit 6 consecutive patients beginning ICI therapy
- 2) Screening labs, including troponin, high sensitivity CRP, and **NT-proBNP**; peripheral blood draw sent to research lab ([name]) for T cell phenotyping.
- 3) Complete PET-CT MFR⁶ immediately before and 4-6 weeks after initiation of ICIs
- 4) Assess change in MFR (per literature 20% or more decreased indicates significant change)⁷
- 5) Continue long-term follow-up of the patients in charts to determine if any develop IRAEs
- 6) For patients who develop myocarditis a FDG PET-CT would be performed to assess for inflammation

E.1 Detailed Methods

1) Recruitment: Investigator [name] has met with hematology team ([name] MD PhD) who will work with his PA team to identify eligible patients for recruitment. Those deemed eligible will be approached during their initial visits with oncology (prior to initiation of ICI.

2): PET-CT MFR methodology (performed during two sessions-one before and one 4-6 weeks after administration of ICI):

A GE Discovery 690XT, Discovery Molecular Insights (DMI) or 710 PET/CT system (GE Healthcare, Waukesha, WI) will be utilized in performing the studies. The imaging system consists of full ring Cerium-doped Lutetium Yttrium Orthosilicate (LYSO) crystals. 128x128 PET matrix size with zoomed 41.9 cm field of view centered over the heart will be used to obtain the PET images. Furthermore, three-dimensional list mode acquisition will be employed. Three-dimensional iterative reconstruction algorithm with time-of-flight correction, CT attenuation, scatter, randoms, normalization, decay and dead time correction will be utilized. Three-dimensional Hanning post-filter with a 10 mm cut-off will also be used.

A 64 slice-spiral CT will be employed with auto exposure control with modulated current in order to maintain consistent noise index (noise index set at 33 with mA range 10-180). For our CT attenuation imaging tube ratio is 0.5 s, kV is 120 and pitch is 0.98. Slice thickness is 3.75 mm and slice increment is 3.27 mm. Matrix size is 512 x 21.

$^{13}\text{NH}_3$ will be administered at rest to allow qualitative and quantitative (rest myocardial blood flow) assessment of myocardial perfusion. Regadenoson will be administered as a stress agent followed by a $^{13}\text{NH}_3$ with subsequent qualitative and quantitative (myocardial blood flow) assessment of myocardial perfusion. MFR will then be determined by assessing the ratio of stress to rest myocardial blood flow.

For those patients who are suspected to have developed myocarditis they will undergo a FDG-PET CT inflammatory protocol. PET/CT parameters will be similar as noted above. However, no stress agent will be used. Furthermore, FDG will be administered per the inflammatory myocardial protocol for assessment of inflammation.

3) Analysis of T lymphocytes in peripheral blood for phenotypic markers via flow cytometry:

Peripheral blood mononuclear cells (PBMC's) will be isolated from whole blood using a Ficoll gradient, counted, and frozen in liquid nitrogen. For analysis, PBMC's will be thawed and plated overnight in complete RPMI media with IL-2 (10u/mL). The following day, cells will be counted and stained with fluorophore-labeled antibodies suitable for flow cytometry, which may include (but are not limited to): CD45 (clone HI30, catalog 304006), CD3 (clone OKT3, catalog 317344), CX3CR1 (clone 2A9-1, catalog 341616), CD11a (clone HI111, catalog 301212), and PD-1 (clone EH12.2H7, catalog 329904) antibodies from BioLegend; CD8 (clone RPA-T8, catalog 557746) and Ki67(clone B56, catalog 562899) antibodies from BD Biosciences; and anti-human granzyme B (clone GB11, catalog NBP1-50071PCP) from Novus. Cells will then be assayed using a Beckman Coulter Cytoflex LX flow cytometer and data analyzed using FlowJo software (BD Biosciences).

3): Statistical Analysis

General Considerations

Continuous data (e.g., age) will be summarized using the following descriptive summary statistics: the number of subjects (n), mean, SD, median, minimum value (min), and maximum value (max). For each continuous variable, the corresponding mean, median, minimum and maximum will be presented to 1 decimal place and the SD to 2 decimal places, unless otherwise specified.

Categorical variables (e.g., qualitative presence or absence of perfusion deficit) will be summarized using counts and percentages. Percentages will be presented to 1 decimal place. Summaries of continuous and categorical data will be presented, as appropriate.

Incomplete/Missing data: Missing data (e.g., dates, post-baseline values) will not be imputed, unless otherwise specified; i.e., all missing values and missing post-baseline values will remain as missing in all statistical analyses and listings, unless otherwise specified.

Outliers: No formal statistical analyses will be performed to detect and/or remedy the presence of statistical outliers.

Additionally, all subject data, including derived variables, will be presented in subject data listings; listings will display all subjects who were randomized or enrolled in the study.

Background Characteristics

Demographics and Baseline Characteristics

Demographics and baseline characteristics (age, sex, race, ethnicity, weight, height and body mass index [BMI]) will be summarized.

Efficacy Analysis

Analysis of Primary Efficacy Endpoint

Nominal continuous variables will be represented as the mean +/- SD and categorical variables will be noted as the number and percentage of total. Pearson chi-square test will be utilized to determine statistical significance for continuous variables whereas a Student's two-sample t-test will be implemented to determine statistical significance for categorical variables. Univariate and multivariate analyses will be performed when relevant. Statistical significance will be set a priori as a p-value less than 0.05. Given that this is a pilot study no power calculation will be performed. All statistical analyses will be performed using JMP Pro 9 (SAS Institute INC. Cary, North Carolina).

Adverse Events Collection:

Adverse Events will be collected only for activities done for research.

The selection of study subjects will be based upon the following inclusion and exclusion criteria:

Inclusion

1. First time administration of ICI
2. Willing and able to return in 4-6 weeks for follow-up study

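### Aim 1 asks whether ICI causes endothelial dysfunction, but a single-group before-after design can only describe a change in MFR, and the plan does not say that other anticancer agents are recorded

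*Combined protocol and SAP*

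**What the plan says.** **Aims.** Section C states Aim 1 causally: "First is to determine if ICI administration causes microvascular damage/endothelial dysfunction". The sentence on Aim 2 opens with 'If so'. It then gives the study the role of a pilot for larger trials "to determine the prevalence of ICI-induced microvascular damage/endothelial dysfunction".

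**Design.** The Brief Synopsis of Methods plans to "recruit 6 consecutive patients beginning ICI therapy", with one PET-CT session before ICI and one 4 to 6 weeks after its start. Item 4 is to assess the change in MFR, with a decrease of 20% or more taken as significant. No control group, untreated cohort or repeat baseline scan is described.

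**Descriptive wording elsewhere.** The Rationale presents the proposal as an assessment of how MFR changes from before to after ICI initiation. The hypotheses in the Abstract and Section B speak of patients who receive or are prescribed ICI.

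**Other agents.** The Rationale says "Endothelial dysfunction has been demonstrated with the use of other multiple chemotherapeutic agents" and that PET-CT has been used to "demonstrate a decrease in MFR in some patients after exposure to doxorubicin but not others". Section D, item 3 of what is known, adds: "PET-CT MFR can be used to detect chemotherapeutic reduction in MFR in patients receiving traditional agents such as doxorubicin".

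**Eligibility, data and analysis.** The only treatment-related criterion is a first ICI. Exclusions concern age, pregnancy or breast-feeding, and consent. The listed baseline characteristics are demographic and anthropometric. Multivariate analysis is planned where relevant, with no covariate named.

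**The concern.** Aim 1 claims something that the design cannot deliver. A fall in MFR after ICI is compatible with an ICI effect, with an effect of another drug, with other change over the interval, and with scan-to-scan variability. Because Aim 2 depends on Aim 1, a descriptive finding could be carried into larger trials as an established causal premise.

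The second part makes the first worse. The protocol itself identifies other chemotherapy as a cause of the same outcome and says the same measure detects it. If a patient receives such an agent around or between the scans and MFR falls, the fall has a competing explanation. Unless that exposure is listed, a reader of the results cannot tell which patients are affected.

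**Working it through.** **Inputs from the protocol.** n = 6, one group, two scans, 20% threshold (Brief Synopsis of Methods); significance at p < 0.05 and no power calculation (Analysis of Primary Efficacy Endpoint). The protocol gives no basis for six, so there is no figure to reproduce. It also gives no SD for the MFR change and no co-treatment rate. SDs below are assumptions, and no co-treatment rate is assumed.

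**Step 1: what the design identifies.** Write each patient's observed change as

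change = a (ICI) + b (other anticancer agents) + c (other change over the interval) + e (scan variability).

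Only the left side is observed, and no group has a = 0. Adding patients averages out e but leaves the mean of a + b + c unseparated. The limit therefore comes from the missing comparator, not from the number six.

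**Step 2: illustration.** Take a = 0 and let b + c shift the mean by m SDs of the change. For a two-sided paired t-test at 0.05 (chosen for illustration; the plan does not specify it), the noncentrality is m√6. The chance of rejecting 'no change' is:

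| m | m√6 | P(reject), ICI effect zero |
|---|---|---|
| 0.5 | 1.22 | 17.1% |
| 1.0 | 2.45 | 50.7% |
| 1.5 | 3.67 | 83.3% |

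Since noncentrality grows with √n, a larger single group would reject more often for the same non-ICI shift.

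**Step 3: the per-patient threshold.** Suppose the true mean change is zero and percent changes are normal with an assumed SD. The chance that at least one of six falls by 20% or more is 1 − [1 − Φ(−20/SD)]^6:

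- SD 10 points: 1 − (1 − 0.0228)^6 = 12.9%
- SD 20 points: 1 − (1 − 0.1587)^6 = 64.5%
- SD 30 points: 1 − (1 − 0.2525)^6 = 82.6%

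So even a patient with no other agent can cross the threshold without an ICI effect.

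**Step 4: what one co-treated patient would do.** Each patient is 1/6 = 17% of the result. Exact (Clopper-Pearson) 95% intervals are:

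- One decrease among six: 1/6 = 17% (0.4% to 64%).
- That patient co-treated and set aside: 0/5 (0% to 52%), upper limit 1 − 0.025^(1/5) = 0.522.
- Another patient, without a decrease, co-treated and set aside: 1/5 = 20% (0.5% to 72%).

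The intervals overlap almost entirely, so the estimate is uninformative either way. What changes is whether the only decrease has a visible competing explanation.

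**Step 5: could existing text capture co-treatment?**

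| Text | Does it reach co-treatment? |
|---|---|
| Inclusion criterion 1, first ICI | No: a first ICI need not be the only agent |
| Inclusion criterion 3, reliance on delta MFR | No: it addresses previous heart conditions, not an exposure during the interval |
| Baseline characteristics | Cancer therapy is not listed |
| Listings of all subject data | They show only what is collected |
| Chart follow-up (Methods item 5) | Stated for IRAEs |
| Multivariate analysis where relevant | No covariate named, and six patients cannot support meaningful adjustment |

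**The case against.** The strongest reply is that this is a labelled pilot with a descriptive purpose. The Rationale, Methods item 4 and the hypotheses all concern change in MFR, so the fault may be one verb in Aim 1. That stands as to seriousness. It does not remove the fault: the pilot role is assigned to Aim 2, on the condition that Aim 1 is answered, and waiving a power calculation excuses the sample size, not the causal claim.

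Several stronger readings are tempting, and the documents do not support them:

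- *The study will report a causal conclusion.* No analysis rule turns a fall in MFR into one. Aim 1 invites over-interpretation but does not compel it.
- *The Section D questions are equally at fault.* "Do ICIs cause microvascular disease/endothelial dysfunction" and "If ICIs do cause microvascular disease/endothelial dysfunction how common is this occurrence" stand under what remains to be discovered. They are gaps in the field, which may properly be causal.
- *Aim 2 asserts ICI-induced damage.* That phrase describes what larger trials would determine. Only the opening condition ties it to Aim 1.
- *Six patients are too few to show causation.* This implies that more would suffice. Step 1 shows otherwise.
- *The results will be confounded by co-treatment.* The documents do not say that any co-treated patient will be enrolled. The gap is in what the plan commits to record.

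It is also fair to say that a sensitivity summary without co-treated patients would add almost nothing beyond a per-patient listing, given Step 4, and that calling such a subset clean could falsely reassure, given Step 3. Both objections stand, and the required fix omits that summary.

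**Conclusion.** The concern holds in two parts. First, Aim 1 as worded cannot be answered by a single-group before-after comparison, whatever its size, and it conflicts with the protocol's own descriptive purpose. Second, the plan names a competing cause of the same finding and does not state that it is restricted, recorded or shown.

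Severity is minor to moderate. The study remains useful as a descriptive pilot. The causal point rests on the design alone and needs no numerical assumption. The rejection and threshold probabilities are illustrations that depend on the assumed shifts and on an SD of 10 to 30 points. The co-treatment part is conditional on such a patient being enrolled, and no likelihood is claimed for that.

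**What to change.** 1. **Wording.** Reword Aim 1 as *describe the change in MFR after ICI initiation*. Remove the 'If so' condition from Aim 2. State that a fall in MFR cannot be attributed to ICI without a comparator.
2. **Listing.** Abstract from the chart every non-ICI anticancer agent, with start and stop dates, from a prespecified lookback before the first scan through the second scan. List it beside each patient's MFR change, and distinguish agents given only before the first scan from those given between scans.

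Rewriting the Section D questions and adding a sensitivity subset are optional.

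**Cost.** A short amendment, slight chart abstraction for six patients whose charts are already followed for IRAEs, and a less ambitious stated aim. Eligibility, recruitment and treatment do not change. The design stays non-causal: the listing makes one competing explanation visible but does not remove the others.

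### The pilot aim hangs on an undefined yes/no answer to Aim 1; p<0.05 in six patients is a poor basis for that answer, and no interval is planned for the change or the decliner proportion

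*Combined protocol and SAP*

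**What the plan says.** Section B (Hypothesis) expects an effect in a subset: "PET-CT MFR will identify a certain proportion of oncologic patients being prescribed ICIs". The abstract likewise expects MFR to fall in some patients.

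Section C (Aims) states Aim 1 as a yes/no question, "First is to determine if ICI administration causes microvascular damage/endothelial dysfunction", and continues "If so, the second aim is to serve as a pilot study for larger trials". Neither sentence says what result would count as a yes.

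The Brief Synopsis of Methods plans to "recruit 6 consecutive patients beginning ICI therapy", with one scan before and one 4-6 weeks after the start of ICI. Its item 4 treats a fall in MFR of 20% or more as a significant change, citing the literature. Item 5, chart follow-up for IRAEs, carries no condition.

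Under Analysis of Primary Efficacy Endpoint: "Statistical significance will be set a priori as a p-value less than 0.05" and "Given that this is a pilot study no power calculation will be performed". Whether tests are one- or two-sided is not stated.

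Under General Considerations, "Categorical variables (e.g., qualitative presence or absence of perfusion deficit) will be summarized using counts and percentages". Continuous data get n, mean, SD, median, minimum and maximum. No confidence interval is planned anywhere.

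**The concern.** The step from Aim 1 to Aim 2 has no criterion. Someone who wants one will find only the p<0.05 rule under the primary endpoint. That rule suits the hypothesis badly: a test of the mean looks for a general shift, whereas the hypothesis is that a minority of patients decline. With six patients such a test will mostly be non-significant even when the hypothesis is true.

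If p<0.05 is not meant, the criterion is open and could be settled after the data are seen.

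The planned output would not correct a misreading. A result of 0/6 would appear as a count and 0.0%, with nothing to show how large a prevalence it leaves open. Section D asks how common the effect is, so the uncertainty around that percentage is what the planners of a larger trial need.

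**Working it through.** The plan gives no power, effect size or SD, so there is no figure of its own to reproduce.

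**Inputs from the documents:** n = 6, paired scans; alpha 0.05; per-patient marker of a 20% or greater fall in MFR.

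**Assumptions:** one third of patients decline; true falls of 20-30% in decliners and no true change in the rest; per-scan CV of 8-15% with log-normal error; two-sided testing unless stated.

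**1. Paired t-test without noise.** Let two of six patients fall by D and four not change.
- Mean change = −D/3.
- Sum of squared deviations = 2(2D/3)² + 4(D/3)² = 4D²/3, so SD = √(4D²/15) = 0.516D.
- SE = 0.516D/√6 = 0.211D, and t = −0.333/0.211 = −1.58 on 5 df, p = 0.17.

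D cancels. A larger fall does not help, because it raises the SD in step with the mean.

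**2. Paired t-test with noise** (simulation on the log scale, 200,000 runs per setting).
- Exactly two decliners: p<0.05 in about 6-9% of runs.
- Each patient declining with probability 1/3: about 9-15%.
- One-sided, random third: about 16-28%.

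**3. Chi-square (uncorrected) of 0/6 at baseline against x/6 at follow-up.**
- x = 2: 12 × (6×2)² / (6×6×2×10) = 2.4, p = 0.12.
- x = 3: 12 × (6×3)² / (6×6×3×9) = 4.0, p = 0.046.

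Three decliners are needed. With error-free classification, P(X ≥ 3 | 6, 1/3) = 32%.

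**4. The per-patient marker, read as at least one observed fall of 20% or more.** The SD of the log ratio is CV × √2, so 0.113 at CV 8% and 0.212 at CV 15%. The threshold is ln 0.80 = −0.223.
- Noise alone, per patient: Φ(−0.223/0.113) = 2.4%; Φ(−0.223/0.212) = 14.6%.
- Noise alone, at least one of six: 1 − 0.976⁶ ≈ 14%; 1 − 0.854⁶ ≈ 61%.
- A random third truly declining, lowest case (fall 20%, CV 8%): per patient (1/3)(0.50) + (2/3)(0.024) = 0.183, so 1 − 0.817⁶ ≈ 70%.
- Highest case (fall 30%, CV 15%): per patient (1/3)(0.736) + (2/3)(0.146) = 0.343, so 1 − 0.657⁶ ≈ 92%.

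This rule usually says yes when a third decline, but it says yes in 14-61% of studies when nobody does.

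**5. What the missing intervals would show** (exact 95%, Clopper-Pearson).

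| Observed | 95% CI |
|---|---|
| 0/6 | 0 to 45.9% |
| 1/6 | 0.4 to 64.1% |
| 2/6 | 4.3 to 77.7% |

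For 0/6 the upper limit is 1 − 0.025^(1/6) = 45.9%. With error-free classification, a true prevalence of 20% gives 0/6 with probability 0.8⁶ = 26.2%; measurement noise moves that figure in either direction. For the mean log ratio, the half-width is 2.571 × SD/√6 = 1.05 SD.

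**The case against.** A reader might infer that the plan itself sets a p<0.05 gate and that the programme would stop on a non-significant result. The documents support neither. No sentence links the condition in section C to the significance level, which is stated generally. The only operational marker for MFR is the per-patient 20% fall, and the hypothesis is also worded per patient. There is no stopping rule: no scan, blood draw or summary depends on the condition, chart follow-up for IRAEs is unconditional, and section B says without condition that the study could be the foundation for larger evaluations.

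The low pass rates are also conditional. The one-third rate, the size of fall and the CV are assumptions. The plan does not name a paired t-test; it names a Pearson chi-square test and a two-sample t-test, attached to the wrong variable types, which is a separate fault. Fixing exactly two decliners gives the low end of the range.

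Finally, much is already planned. With six patients, the listings of all subject data would let a reader see each change, and an exact interval can be computed from x/6 alone.

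All of this stands, and it limits the point to an undefined criterion plus missing intervals. It does not remove the point. The per-patient marker is not adopted as the answer to Aim 1, and if it were, noise would often satisfy it. That an interval can be derived is also no substitute for reporting it beside the percentage.

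**Conclusion.** The concern holds in a limited form. Aim 2 is conditional on a question whose answer is not defined, and the one decision rule on offer is unsuited to a minority effect in six patients. If p<0.05 is used and about a third of patients decline, a two-sided paired t-test succeeds in about 6-15% of studies and the chi-square comparison in about 32%. These figures rest on the assumed one-third rate; the t-test range also rests on falls of 20-30% and a per-scan CV of 8-15%, and the chi-square figure on error-free classification. Under the 20% marker, at least one drop is seen in about 70-92% of studies on the same assumptions, and in 14-61% through noise alone.

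The missing intervals need none of these assumptions: 0/6 observed drops is compatible with a proportion of up to 46%. So a non-significant result, or 0.0%, should not be read as showing no damage.

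**What to change.** In section C, remove the condition so that Aim 2 stands whatever the result of Aim 1.

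In the statistical section, add for patients with both scans:

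- the mean and SD of the within-patient log MFR ratio (follow-up over baseline), with a 95% CI for the mean;
- the number and proportion with an observed MFR fall of 20% or more, with an exact 95% CI;
- a note that this interval covers observed drops, including measurement noise, and not confirmed damage;
- a statement that a non-significant result in six patients is not evidence of no effect, and that planning of a larger trial rests on these estimates.

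The cost is a few words in the Aims, a short paragraph in the analysis section and a few output lines. No new patients, scans or data are needed.

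### A fall in regadenoson MFR cannot by itself separate endothelial dysfunction from other causes of a lower flow ratio, and an unchanged MFR does not show an intact endothelium

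*Combined protocol and SAP*

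**What the plan says.** C. Aims sets the first aim: "First is to determine if ICI administration causes microvascular damage/endothelial dysfunction". B. Hypothesis uses the same compound term for what MFR is expected to identify. The Abstract words the inference differently, expecting that "MFR will decrease in some patients receiving ICI thereby representing early, subclinical myocardial injury", and it also credits quantitative PET-CT with assessing endothelial function.

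E.1 Detailed Methods, item 2, describes the measurement. After a rest acquisition with 13NH3, "Regadenoson will be administered as a stress agent followed by a" further 13NH3 injection, and "MFR will then be determined by assessing the ratio of stress to rest myocardial blood flow". The only other scan, FDG PET-CT for suspected myocarditis, adds no second stimulus: "However, no stress agent will be used". The decision rule is in E. Brief Synopsis of Methods, item 4: "Assess change in MFR (per literature 20% or more decreased indicates significant change".

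A. Rationale gives the link from this ratio to the endothelium. PET-CT is said to "assess total myocardial blood flow, specifically myocardial flow reserve (MFR,) including assessment of the endothelium". The laboratory tests named in the synopsis are troponin, high-sensitivity CRP and NT-proBNP, and the flow cytometry concerns T cells. No test directed at the endothelium is named, and no rule says how a fall in MFR is to be attributed to one cause rather than another.

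**The concern.** The conclusion is about a tissue and the measurement is a ratio of two flows. On the Rationale's own wording, the endothelium is one part of what MFR reflects, and a change in the whole does not show which part changed.

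Two errors are open. A fall in MFR could be reported as endothelial dysfunction when it came from a higher rest flow, or from a lower stress flow with another cause. A stable MFR could be read as evidence that the endothelium is unharmed when the ratio may simply be insensitive to that injury. Both matter beyond this pilot. The second aim follows only if the first is answered yes, and the Hypothesis offers the study as a foundation for larger evaluations. A wrong label would carry into the decision to run the next trial and into its choice of endpoint.

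**Working it through.** The plan gives no calculation on this point, so there is no figure of its own to reproduce. Two inputs come from the documents: MFR = stress flow / rest flow (E.1, item 2) and the 20% criterion (synopsis, item 4).

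**Step 1. What produces a 20% fall? (documents only)**

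The follow-up MFR divided by the baseline MFR equals (stress-flow ratio) / (rest-flow ratio), each ratio being follow-up over baseline. The criterion is met when this is 0.80 or less.

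- Stress flow unchanged: 1 / r = 0.80, so r = 1/0.80 = 1.25. A 25% rise in rest flow is enough.
- Rest flow unchanged: a 20% fall in stress flow is enough, whatever its cause.
- Both change: rest flow up 10% and stress flow down 12% gives 0.88/1.10 = 0.80.

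The three patterns have different meanings but give the same MFR result. Inclusion criterion 3 admits patients with previous heart conditions, on the argument that the change in MFR is what is assessed. Taking the change removes a stable difference between patients at baseline. It does not show why MFR moved within a patient.

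**Step 2. What would endothelial loss do to MFR? (assumptions needed)**

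Let M be the baseline MFR and f the share of the stress increment (M − 1) that depends on the endothelium. Neither is in the documents; both are varied here. With rest flow unchanged, complete loss of that share lowers MFR from M to M − f(M − 1), a relative fall of f(M − 1)/M. A 20% fall therefore needs f ≥ 0.20 × M/(M − 1).

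| Assumed baseline MFR | fall, f = 0.1 | f = 0.2 | f = 0.3 | f = 0.4 | share needed for 20% |
|---|---|---|---|---|---|
| 2.0 | 5.0% | 10.0% | 15.0% | 20.0% | 0.40 |
| 2.5 | 6.0% | 12.0% | 18.0% | 24.0% | 0.33 |
| 3.0 | 6.7% | 13.3% | 20.0% | 26.7% | 0.30 |
| 3.5 | 7.1% | 14.3% | 21.4% | 28.6% | 0.28 |

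Example at M = 2.5 and f = 0.4: 2.5 − 0.4 × 1.5 = 1.9, and 1.9/2.5 = 0.76, a fall of 24%.

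If only half of the endothelial share is lost, each fall is halved. At f = 0.5 the fall is then 0.5 × 0.5 × (M − 1)/M, which is 12.5% at M = 2.0 and 17.9% at M = 3.5, still short of 20%.

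So a small share hides even total endothelial loss from the criterion, and a moderate share lets total loss reach it. Without a value for f, the plan has no basis for reading a preserved MFR as a healthy endothelium.

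**The case against.** A reader might infer something stronger: that regadenoson dilates the coronary bed largely without the endothelium, so MFR in this trial cannot support any endothelial conclusion. The documents do not carry that. They say nothing about how regadenoson dilates vessels or what share of its effect depends on the endothelium. They assert the opposite link, with citations that cannot be checked here. The table above also contains combinations in which endothelial loss does reach 20%. The supportable claim is that MFR is not specific to the endothelium, and of unknown sensitivity to it.

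Three further points in the plan's favour stand:

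- The planned conclusion is a compound term, and nothing here removes its microvascular half.
- The mechanism in the Rationale, that dysfunction "is likely due either to endothelial cell death or reduced nitric oxide availability", is given for other chemotherapeutic agents. It should not be read as the stated mechanism for ICIs.
- The plan nowhere says that an unchanged MFR will be reported as absence of endothelial injury. That risk comes from its silence. The laboratory list is also introduced as non-exhaustive, so the fair statement is that no endothelial marker is named.

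It can also be said that this is a six-patient pilot and that all subject data, including derived variables, will be listed. The rest and stress flows may therefore appear in listings. But the Statistical Analysis section does not call for their changes to be summarised beside MFR or used in interpreting a fall. The pilot label does not help either, since the study's purpose is to inform a larger one.

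The citations for PET and the endothelium do not answer the point. A measurement that includes the endothelium is not thereby specific to it.

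**Conclusion.** The concern holds as one of non-specificity. From the documents alone, a fall of 20% or more in this ratio does not locate the change in the endothelium: a 25% rise in rest flow, a 20% fall in stress flow from any cause, or a mixture of the two meets the criterion equally.

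The converse is conditional. For an assumed baseline MFR of 2.0 to 3.5, complete loss of endothelium-dependent dilation stays below 20% whenever its share of the stress increment is under 0.40 to 0.28 respectively. The true share and baseline are not in the documents, so it is not established that MFR would miss such injury, only that an unchanged MFR does not exclude it.

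The study remains able to show whether MFR falls in some patients after ICI initiation. What needs to change is the conclusion attached to that result.

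**What to change.** 1. In B. Hypothesis and in the first aim under C. Aims, name the measured outcome as a reduction in regadenoson MFR. Give microvascular damage/endothelial dysfunction as a possible explanation that the study does not separately test.
2. Bring the Abstract's reference to endothelial function into line with this. Leave the questions under What remains to be discovered (D. Innovation) as background, since they are research questions and do not describe the measurement.
3. State that an unchanged MFR will not be reported as absence of endothelial injury.
4. In the Statistical Analysis section, add the change in rest flow and the change in stress flow, per patient and summarised, beside the change in MFR, so that a fall driven by rest flow is visible.

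The cost is a narrower headline claim and slightly more reporting. Both flows are already measured to form the ratio, and the stress agent and procedures stay as they are.
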